Efficacy and Safety of the Melanocortin Activator Bupropion in Treating Binge Drinking

NCT number NCT03169244 **Document Date** 08/26/2019

Protocol Version 3.1

Efficacy and Safety of the Melanocortin Activator Bupropion in Treating Binge Drinking

Overall Concept: The current proposal represents an innovative pharmacological approach to the treatment of binge drinking that derives from preclinical findings from the laboratory of [name], one of the proposal's consultants. [name] found that a melanocortin agonist, melanoton II, potently suppresses binge drinking (Navarro et al, 2015) in a mouse model of binge drinking. Because the antidepressant bupropion has been shown to activate melanocortin systems in brain (Greenway et al, 2009) [name] lab also studied the effect of bupropion on binge-drinking in their model and showed that bupropion significantly reduced binge-drinking at doses that were lower than those that suppress appetite (unpublished data). Because bupropion is a clinically available and FDA approved medication [name] initiated a discussion with our group to consider a clinical trial of bupropion for binge drinking. Navarro et al (2015) found evidence that using a melanocortin agonist with an opioid antagonist enhanced the potency of the opioid antagonist to suppress binge drinking. In addition to a direct effect on binge drinking may have value in *preventing* progression of alcohol use from binge drinking to dependent level drinking (Thiele, 2012; Navarro et al, 2015)—potentially, a very important finding for clinical care.

The current proposal uses this preclinical and clinical data to design a groundbreaking translational placebo-controlled, Phase IIa clinical trial to 1) assess for an efficacy signal of the melanocortin activator bupropion in binge drinking individuals who have not developed physical dependence on alcohol and 2) to assess for a modulating effect of coexisting nicotine dependence on possible bupropion response. The current proposal is highly novel as it tests the efficacy of activating the melanocortin system in an understudied population (binge drinkers without physical dependence on alcohol.

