
The current proposal will conduct the first human trial to test the novel preclinical finding that activating melanocortin systems in brain with/without opioid blockade potently reduces binge drinking. Identification of a potential efficacy signal would be significant as it would not only demonstrate that activation of melanocortin systems with/without opioid blockade has potential for therapeutic application for binge drinking in humans but would increase awareness of a biomedical component of binge drinking which could positively affect medical clinicians' attitudes and potentially increase identification and treatment efforts.

Nicotine as a potential moderator of bupropion response: Two recent reports have suggested that comorbid nicotine dependence may be associated with a reduction in drinking with pharmacotherapy (naltrexone) in alcohol use disorders (Fucito et al, 2012; Anton et al, Abstract, Research Society Alcoholism, 2016). The reasons for this are unclear though Fucito et al (2012) have noted that co-existing nicotine use may be associated with more severe alcohol use disorders that are more responsive to pharmacotherapy perhaps because of differences in neurobiology. Given that bupropion has been shown to treat nicotine IRB #16-1064 Master Protocol v.3

dependence and has been approved by the FDA for this purpose there is an interest in whether co-existing nicotine dependence has any impact on possible drinking responses to bupropion. Accordingly, we will stratify by nicotine dependence, attempt to recruit about 50% of subjects with nicotine dependence and will monitor for changes in nicotine use.

Innovation

The present application is innovative in two major areas: 1) it represents the first clinical test of the exciting preclinical finding that activating melanocortin systems potently counteracts binge drinking and 2) it represents one of the first clinical trials to investigate the efficacy of pharmacotherapy for binge drinking. These innovations have the potential to affect clinical practice for the binge drinking patient.

Innovation 1. First proof of concept trial to translate to humans the preclinical finding that activation of melanocortin systems with/without μ -opioid receptor antagonism reduces binge drinking

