**Trial Design**: The design is a 1:1 random assignment to placebo or bupropion XL (300mg/d). [name], the study biostatistician, will prepare the randomization schedule and include blocking by gender. Randomization will be based on a stratified block design, with gender and nicotine dependence as the IRB #16-1064 Master Protocol v.3

stratification variable given some evidence of a moderating effect of nicotine dependence on response to alcohol pharmacotherapy (Fucito et al, 2012).

Bupropion XL will be initiated at 150 mg/d on Days 1-4 and increased to 300 mg/d for Days 5-84. Medication is reduced to 150mg/day for 3 days before being stopped at Week 12 UNC Hospital's Investigational Drug Services (IDS) will prepare opaque capsules containing bupropion XL 150/300 mg and matching placebo. Capsules will be inserted into blister packs with each pack containing 1 week of medication. The IDS will receive the randomization schedule from our statistician [name] and prepare the blister packs according to the blocked schedule with blocking for gender

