Recruitment, Telephone Screen, and Full Eligibility Screening: Subjects will initially be prescreened by phone and then at full screening read and sign the informed consent. A breathalyzer test will be administered (must be 0.00 gms/dl to give informed consent), height, weight and BMI recorded and a medical history and examination completed. Over-the-counter and prescription medication use will be recorded and nicotine use documented (Heatherton et al, 1991). CBC with differential; serum bilirubin, AST, ALT, GGT, sodium, potassium, chloride, blood urea nitrogen, creatinine, glucose; and urinalysis and urine toxicology completed. Women will be given a urine pregnancy test (U β -HCG) at screening and at weeks 4, 8, and 12 and at the initial treatment visit if it is more than 10 days from the screening visit. Trained interviewers will conduct the psychiatric screening interview using the M.I.N.I. (Sheehan et al., 1998). The SCID Substance Use Disorders Module to establish DSM-V criteria for alcohol use disorders (First et al, 2016) will be administered by either [name] o another doctor listed on the IRB protocol. The study coordinator will conduct the pretreatment 90day Timeline Followback (TLFB) interview to identify amount of alcohol consumed and timeframe of consumption (Sobell et al, 1988 and personal communication). A binge drinking episode requires a minimum of 5/4 (men/women) standard drinks consumed over about a two hour period, i.e. consuming a bottle of wine over five hours would not be coded as a binge drinking day. The Penn Alcohol Craving Scale (PACS) (Flannery et al, 1999) and the University of Rhode Island Change Assessment (URICA) (Diclimente and Hughes, 1990) will be completed and treatment goal—abstinence vs. reduction— recorded.

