Initial Treatment Visit (within 21 days screening): Eligible individuals will *not be required to abstain from drinking alcohol* prior to randomization. The study coordinator will administer a breathalyzer test (BAC must be ≤0.04 gms/d) and complete assessments as outlined in Table 1, Protection of Human Subjects. A salivary sample for cotinine to be assayed at UNC will be taken. A 1-week blister pack of bupropion-XL or placebo with written instructions will be dispensed from the Investigational Drug Services according to the randomization block. A 1-week back-up blister pack will dispensed once the participant reaches the maintenance dose in case of delayed appointments or lost doses. Bupropion-XL will be titrated with 150 mg given daily for 4 days followed by 300 mg/d. Participants will be given a calendar style diary to track pill taking, drinking quantity/timing, intoxication and any side effects. Finally, participants will receive Medical Management from a trained clinician.

Subsequent Treatment Visits: See Table 1 in Protection of Human Subjects for a summary of procedures and assessments. Salivary cotinine samples will be obtained at weeks 4, 8 and 12. TLFB and PACS are gathered each visit. Medical monitoring will be conducted by study physicians and will consist of review of vital signs, concomitant medication use, and general inquiries into side effects. Blood pressure readings of >100mm Diastolic or >160mm Systolic will be automatically rechecked. If a participant has sustained, recurrent blood pressure readings above this limit, their medication will be tapered and stopped. The physician may recommend that medication be held or reduced for a period of time to deal with an adverse event, e.g. nausea. The Visit Window is defined as +/-3 days for weekly visits and +/-7 days for visits that occur every 2 weeks.

IRB #16-1064 Master Protocol v.3

Missed Visits are expected. Participants can remain in the study as long as they do not miss more than 2 consecutive visits. If a missed visit has a safety lab test, every effort will be made to schedule the subject as soon as possible to obtain the sample. One month and three months following the last visit subjects will be contacted to update drinking (TLFB), adverse effects and medications.

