an analytical procedure which maximizes the statistical power. The Institute of Medicine recommends several approaches, including clustered models, to maximize information from small trials and increase statistical power (Institute of Medicine, 2001). Using the full sample (N=50), we will fit a Mixed Effects Model (MEM) (Schwarz, 1993)) on: %Binge Drinking Days, drinks/binge drinking day, GGT outcomes with the focus on the linear contrasts within the MEM framework examining the superiority of bupropion to placebo. Our modeling will not focus on statistical significance but rather derive confidence intervals for the respective contrasts within the MEM framework examining the superiority of bupropion to placebo MEM accommodates the within-subject correlation of the repeated assessments (weekly for TLFB measures). MEM allows for the inclusion of potential predictors and covariates such as cotinine levels, medication compliance, demographics, and baseline clinical measures such as motivation. Pattern-mixture models (Hedeker & Gibbons, 1997 & 2006) will be used within the MEM structure to assess whether linear contrasts are dependent on attrition/missing data patterns. The pattern-mixture model is dependent on the number of distinct missing data patterns. With this limited sizes study, we will define the patterns as completers vs non-completers as was done by Hedeker & Gibbons (1997,2006). An assessment of significance will not be made but rather we will derive effect sizes of the respective bupropion and placebo contrast for both completers and dropout. With the limited sample and therefore, limited sample per pattern, we realize the respective confidence intervals will be wide. An additional benefit of the MEM is, it will allow us to assess for possible moderators. A moderator is a baseline measure or prerandomization characteristic that has a differential effect on outcome across intervention condition (Kraemer et al., 2002). Moderators are typically defined as variables that significantly interact with condition (Baron & Kenny, 1986; Holmbeck, 1997). The particular moderator of interest is use of nicotine. Assessment of moderation will be made by augmenting our MEM outcome analyses to include the interaction of the effect of assignment (bupropion vs placebo) intervention with the use of nicotine. In a sufficiently sized study, we will have a significant moderator of the assignment effect if the interaction term is significant (Kraemer et al., 2002), where statistically significant interactions would be interpreted by plotting simple regression lines for use versus non-use of nicotine (Holmbeck, 1997; Aiken & West, 1991). With the small sample, we will derive a confidence interval for the respective interaction effect, namely the difference of the differences (the difference between buproprion versus placebo for nicotine users versus the difference between buproprion versus placebo for the nicotine abstainers). Subsequently, we will perform a corroborative set of analyses, in accordance with Kianfiard & Islam (2011), where summary measures over the entire TLFB period are derived. Simple ANOVA/ANCOVA models will be used to perform the above analyses with the model structure producing confidence intervals for both the buproprion versus placebo contrast, as well as the moderation assessment.

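### Aim 2 and the randomisation strata concern nicotine dependence, but every moderation model contrasts nicotine users with abstainers; the moderator should be the dependence stratum

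*Combined protocol and SAP*

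**What the plan says.** The design side of the document speaks of dependence:

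- **Overall Concept, aim 2:** "to assess for a modulating effect of coexisting nicotine dependence on possible bupropion response".
- **Nicotine as a potential moderator of bupropion response:** after noting that bupropion is approved for nicotine dependence, the text says "there is an interest in whether co-existing nicotine dependence has any impact on possible drinking responses to bupropion". It then commits the trial: "we will stratify by nicotine dependence, attempt to recruit about 50% of subjects with nicotine dependence".
- **Trial Design:** "Randomization will be based on a stratified block design, with gender and nicotine dependence as the" stratification factors.

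The analysis side speaks of use:

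- **Sample Size per Group** argues cell sizes from an assumed 2:1 ratio of nicotine usage.
- **Statistical Analysis:** "The particular moderator of interest is use of nicotine". The interaction is defined as the bupropion-placebo difference among nicotine users minus the same difference among abstainers. The ANOVA/ANCOVA models repeat this moderation assessment, and the logistic, Cox and ordinal models add an interaction of assignment with nicotine use.

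On measurement, the screening section says only "prescription medication use will be recorded and nicotine use documented", with a citation to an instrument. For the Initial Treatment Visit the plan states: "A salivary sample for cotinine to be assayed at UNC will be taken". The available text gives no cut-off for dependence and no definition of user or abstainer. The assessment table to which the visit section refers is not in the text.

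**The concern.** Dependence and use divide participants differently wherever someone uses nicotine without being dependent. Such a person is randomised in the non-dependent stratum. Since they are not an abstainer, the moderation models place them with the dependent participants. The interaction interval then does not estimate the aim 2 contrast, and its grouping is not the one stratified at randomisation.

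One of the trial's two stated aims is affected. Because the plan reports estimates and intervals rather than tests, a reader must be able to tell which population contrast an interval describes. As written they cannot, and the analyst has no stated rule for classifying non-dependent users.

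**Working it through.** **The plan's own figure.** Sample Size per Group gives at least 7-10 per arm by nicotine use, from 30 per arm at 2:1. The expected smaller cell is 30 × 1/3 = 10, the upper end of that range; the lower end, 7, equals the minimum cell size the plan cites. The figure reproduces, but it counts users. The 50% dependence target gives 30 × 1/2 = 15. With the N = 50 of the Statistical Analysis section (25 per arm at 1:1), the corresponding cells are 25/3 = 8.3 and 25/2 = 12.5.

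**Inputs for the illustration.**

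- From the plan: dependent share *d* = 0.5 (the recruitment target) and N = 50.
- Assumed: all dependent participants use nicotine, and the use share *u* is two-thirds, with 0.50 to 0.75 as the range. Two-thirds is what 2:1 gives if users are the larger side, which the plan does not say.
- Let the treatment effect relative to that in abstainers be 1 in dependent participants and *k* in non-dependent users (*k* = 0: like abstainers; *k* = 1: like dependent participants).

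**Participants analysed outside their stratum** = 50(*u* − *d*): 0 at *u* = 0.50, 5 at 0.60, 8.3 at 0.667 and 12.5 at 0.75.

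**The two contrasts.**

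- Users versus abstainers: *d*/*u* + (1 − *d*/*u*)*k*
- Dependent versus non-dependent (aim 2): 1 − *k*(*u* − *d*)/(1 − *d*)

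At *u* = 0.667 these become 0.75 + 0.25*k* and 1 − 0.333*k*:

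| *k* | User contrast | Aim 2 contrast | Ratio |
|---|---|---|---|
| 0 | 0.75 | 1.00 | 0.75 |
| 0.25 | 0.81 | 0.92 | 0.89 |
| 0.50 | 0.88 | 0.83 | 1.05 |
| 0.75 | 0.94 | 0.75 | 1.25 |
| 1 | 1.00 | 0.67 | 1.50 |

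They are equal when 0.25 = 0.583*k*, that is *k* = 0.43. Over *k* = 0 to 1 the ratio runs from 0.83 to 1.25 at *u* = 0.60 and from 0.67 to 2.0 at *u* = 0.75. At *u* = 0.50 it is 1 throughout.

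**Absolute size.** Suppose the treatment effect differs by 0.5 SD between dependent participants and abstainers. At *u* = 0.667 the gap between the two contrasts runs from 0.5 × (0.75 − 1.00) = −0.125 SD to 0.5 × (1.00 − 0.667) = +0.167 SD.

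**Precision for comparison.** With one summary value per person, the 95% half-width is *t*(0.975, 46) × SD × √(Σ 1/*n*) over the four cells:

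- four cells of 12.5: 2.013 × 0.566 = 1.14 SD
- cells of 16.7, 16.7, 8.3 and 8.3: 2.013 × 0.600 = 1.21 SD

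The larger gap is about one-seventh of the half-width (0.167/1.14 = 0.15).

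**The case against.** The best reply is that the authors use the two words for one variable. The nicotine rationale reports earlier findings for dependence and then explains them with "co-existing nicotine use may be associated with more severe alcohol use disorders". The screening section describes its nicotine assessment as documenting use, and the dependence stratum presumably comes from that record. No section describes a group of non-dependent users or two nicotine classifications. This reading is possible, and under it the numerical effect is zero. But nothing in the documents equates the terms, and naming abstainers as the comparator goes beyond loose wording, because a non-dependent person need not be an abstainer.

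Second, stratification is not needed for a valid interaction. Within any group defined at baseline, bupropion and placebo remain randomised comparisons, so those comparisons are not biased. That stands; what is lost is the match to aim 2 and the stratified balance on the analysed factor.

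Third, the gap is small against the interval, and the analyses are exploratory and unpowered. That also stands, and it limits the consequence. It does not tell the reader which contrast the interval is for.

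Finally, the illustration needs users to be the larger side of 2:1. If users were one-third of participants, half could not be dependent users. The illustration therefore shows scale only, and a cut-off may exist in the table that is not in the text.

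**Conclusion.** The concern holds. The aim, target and strata are set by dependence and every moderation model by use, and no section reconciles them. Taken literally, the plan estimates a different contrast from aim 2 whenever non-dependent users enrol. The documents determine neither the size nor the direction. Under the stated assumptions the user contrast is 0.75 to 1.5 times the aim 2 contrast (0.67 to 2.0 times at a 75% use share); the effect is zero if one variable is meant or all users are dependent. The consequence is for the meaning of the moderator estimate. No formal test or power claim is affected. The change should be made; confidence is medium because the loose-wording reading cannot be excluded.

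**What to change.** In the Statistical Analysis section, name the baseline nicotine-dependence stratum used at randomisation as the moderator in all models: mixed effects, ANOVA/ANCOVA, logistic, Cox and ordinal. Report the interaction interval for dependent versus non-dependent participants. This answers aim 2 as written and fits the plan's own definition of a moderator as a characteristic fixed before randomisation.

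State the instrument and cut-off that define the stratum. Keep baseline use or baseline cotinine as a labelled secondary split; it is the better contrast if any use, rather than dependence, modifies the effect.

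In Sample Size per Group, state which side of the 2:1 ratio is users and how it relates to the 50% target. The two figures can coexist if 2:1 is a conservative planning assumption.

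The cost is protocol and SAP wording only. The stratum must be known at randomisation and the baseline cotinine sample is already planned, so no new data are needed.

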Innovation 2: One of the first clinical trials to investigate the efficacy of pharmacotherapy for binge drinking. As noted earlier, there has been very limited effort towards identifying pharmacological agents that help with binge drinking, particularly in younger populations. The O'Malley et al (2015) trial may be the first placebocontrolled trial in young (18-25 years), heavy drinkers and it did find evidence that naltrexone reduced drinks/drinking day. Given that the prevalence of binge drinking peaks in the 18-34 year age range and is commonly not associated with physical dependence it is important to conduct clinical trials in populations with these characteristics. The current proposal will therefore focus on subjects ages 21-44 years and will exclude those with overt physical dependence on alcohol.

IRB #16-1064 Master Protocol v.3

Targeting the binge drinking population moves the field towards the concept of using pharmacotherapy to treat early phases of alcohol use disorders and potentially reduce the likelihood of individuals progressing from binge-drinking to overt physical dependence. While still a theoretical concept this is a highly innovative idea and one that could have profound implications for clinical management, see Thiele (2012).

Research Approach

The proposed clinical trial will be the first randomized, double-blind, placebo-controlled Phase IIa trial examining the efficacy and tolerability of the melanocortin activator bupropion along with Medical Management for binge drinking with or without mild/moderate alcohol use disorder. The trial will include 12 weeks of medication administration and a 30-day (safety) and a 90 day (durability) follow-up to assess for delayed adverse events and post-medication drinking behavior.

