Medical Management Intervention: The psychosocial support for the study will be Medical Management (MM) (Pettinati et al, 2005). Drs. [name], [name], [name] and [name] will conduct MM. Drs. [name] and [name] have been trained in MM by [name] and again by [name] of the University of Pennsylvania where [name] was trained as well. [name] has been trained in MM by [name]. MM sessions average 10-15 minutes and focus on three main areas: (1) feedback on consequences of drinking; (2) encouraging compliance with medication/addressing compliance problems and (3) encouraging progress towards drinking goal— reduction or abstinence are acceptable. 10% of sessions will be audiotaped and reviewed to enhance fidelity.

Medication Compliance Monitoring: Participants will record their pill taking in calendar-style diaries that will be provided and collected at each visit. Pills will be distributed in blister packs that will be returned to the study coordinator to reconcile any unused medication from the returned blister packs with participants' diary records.

Statistical Plan and Data Analysis

Outcome Variables: Key outcome variables include frequency of binge drinking, intensity of binge drinking, treatment response, and GGT levels. Frequency is assessed as number of binge episodes/time in trial controlling for missing data (see Statistical Analysis). Intensity of binge drinking is the number of drinks/binge drinking day. Response is defined as no binge drinking in final 6 weeks. Consequences of binge drinking and craving for alcohol will be examined.

Sample Size per Group: In the assessment of feasibility, we need sufficient size to fit our respective models and ensure adequate coverage of our confidence intervals. VanVoorhis and Morgan (2007) provide guidance with respect to minimal sample size needed for differences between groups. They recommend that the groups be no lower than 7 per cell. Our aim is on the effectiveness of bupropion versus placebo in addition to the examination of a potential moderation effect attributable to nicotine use. Assuming a 2:1 ratio between nicotine usage, a sample size of 30 per arm should ensure at least 7-10 per treatment arm as a function of nicotine use. Additionally, our proposed sample size of 30 per treatment arm is in agreement with Sugden et al. (2002) minimum sample size to ensure adequate coverage of nominal 95% confidence intervals, which require n> 28 under minimal skew.

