
Response, i.e. no binge drinking days in final 6 weeks of medication, tolerability measured via retention time, and number of adverse events reported will be examined with Logistic regression, Cox-Regression, and Ordinal-regression models, respectively with the same contrast comparisons as above focused on the derivation of confidence intervals for the respective contrasts. Moderation of nicotine use will follow the procedure as discussed earlier, where the respective models will be augmented to include the interaction of nicotine use with assignment, with the derivation of the confidence interval for the differences as described above.

DATA MANGEMENT PLAN

The Database will be configured in Microsoft Access or Excel. Discrepancies will be examined and additional data checks completed as indicated. A closed and password-protected data entry system will be used and only

certified study personnel will be able to enter or edit data. Data and user stamping are used to create an audit trail. Range checks, review screens, and error trapping routines are built into the system as quality control procedures. Hardcopy data summaries will be available to the investigators for data analyses. As a final check on data integrity, the investigators and study coordinator will check these outputs against the raw data and resolve any discrepancies. We will be asking subjects to fill out self-ratings on a tablet mobile device. The ratings will be in the form of Qualtrics surveys. No identifying data will be entered into the tablet, just a subject ID number.

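### Adverse-event counts are compared by ordinal regression with no allowance for time observed, so unequal dropout would make the arm that loses more people look safer

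*Combined protocol and SAP*

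**What the plan says.** The last paragraph of Statistical Analysis lists response first, then retention time as the tolerability measure, and then says that the "number of adverse events reported will be examined with Logistic regression, Cox-Regression, and Ordinal-regression models", to be taken respectively. Response is therefore paired with logistic regression, retention time with Cox regression, and the AE count with ordinal regression. All three are reported "with the same contrast comparisons as above focused on the derivation of confidence intervals for the respective contrasts". The only stated addition to these models is the nicotine-by-treatment interaction. No exposure term, person-time rate or AE counting window appears.

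Two other parts of the plan do deal with unequal observation, but only for drinking outcomes:

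- Outcome Variables: "Frequency is assessed as number of binge episodes/time in trial controlling for missing data".
- Statistical Analysis, on pattern-mixture models: these "will be used within the MEM structure to assess whether linear contrasts are dependent on attrition/missing data patterns". The AE model lies outside the mixed-effects structure.

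Subsequent Treatment Visits states "Missed Visits are expected", ends participation after more than two consecutive missed visits, and has side effects asked about at visits. Research Approach gives the observation periods: "The trial will include 12 weeks of medication administration and a 30-day (safety) and a 90 day (durability) follow-up". Subjects are also contacted one and three months after the last visit to update adverse effects. The plan does not say whether early leavers are contacted on that schedule, or whether AEs found then enter the count.

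**The concern.** A person who leaves early has had less time in which to report AEs. The ordinal model nevertheless scores that person's low count in the same way as a completer's low count. If the arms lose people at different rates, the model compares unequal amounts of observation and attributes the difference to treatment.

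The plan commits itself to confidence intervals in place of significance tests, so an interval centred in the wrong place damages the very result it promises. The awkward case is one in which people leave an arm because they feel unwell: the same departures lower that arm's AE count. The plan adjusts its drinking count for time in trial and does not do so for its harm count.

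**Working it through.** **No figure to reproduce.** The documents give no AE rate, dropout rate or precision target for this analysis. The figures below come from simulation under stated assumptions.

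**Inputs from the documents.** 12 weeks of medication; 1:1 allocation; N = 50 in Statistical Analysis, hence 25 per arm; ordinal model on arm alone.

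**Assumptions.** 1.5 or 3 AEs per person per 12 weeks on placebo (Poisson); exponential dropout reaching a proportion d by week 12; AEs counted only until the person leaves. Timing is either a constant rate or front-loaded, with 60% of AEs in the first 2 weeks.

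**Step 1: time observed.** Mean weeks on study = 12d / (-ln(1 - d)).

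- d = 10%: 1.2 / 0.105 = 11.4
- d = 30%: 3.6 / 0.357 = 10.1
- d = 50%: 6.0 / 0.693 = 8.7

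With equal true rates, the ratio of mean counts is therefore about 10.1/11.4 = 0.89 at 10% v 30% and 8.7/11.4 = 0.76 at 10% v 50%. A cruder scheme, in which all leavers go at week 4, gives 0.7 x 12 + 0.3 x 4 = 9.6 weeks against 0.9 x 12 + 0.1 x 4 = 11.2 weeks, a ratio of 0.857. The ordinal model reports an odds ratio and not a ratio of means, so it was fitted directly.

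**Step 2: the planned model and an offset model, 20,000 per arm.** Ranges run over the two assumed AE rates. Ratios are bupropion v placebo.

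| Dropout, placebo v bupropion | True rate ratio | Ordinal OR, constant rate | Ordinal OR, front-loaded | Poisson offset rate ratio, front-loaded |
|---|---|---|---|---|
| 10% v 30% | 1.00 | 0.70-0.77 | 0.82-0.84 | 1.04-1.05 |
| 10% v 50% | 1.00 | 0.48-0.58 | 0.65-0.73 | 1.14 |
| 30% v 10% | 1.00 | 1.31-1.42 | 1.18-1.28 | 0.95-0.96 |
| 10% v 30% | 1.30 | 1.25-1.34 | 1.49-1.79 | 1.36-1.39 |
| 10% v 50% | 1.30 | 0.89-0.90 | 1.23-1.35 | 1.46-1.48 |

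- With 20% dropout in both arms, equal rates and constant timing, the ordinal OR is 0.98-1.01.
- Without dropout, a true rate ratio of 1.30 gives an OR of about 1.8 (1.5 AEs) or 2.3 (3 AEs). These are the benchmarks for the last two rows.
- Under a constant rate, the offset model returns 0.99-1.01 for a true 1.00 and 1.28-1.30 for a true 1.30 at every dropout pair.
- If AEs themselves trigger dropout (18% v 33%, equal AE rates), the ordinal OR is 0.73 and the exposure-based rate ratio 0.98.

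**Step 3: interval coverage at 25 per arm.** 600 trials, 3 AEs per 12 weeks, constant rate. Coverage of the OR that would hold without dropout, for a nominal 95% interval:

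| Dropout | True ratio 1.00 | True ratio 1.30 |
|---|---|---|
| 20% v 20% | 94% | 94% |
| 10% v 30% | 90% | 82% |
| 10% v 50% | 70% | 46% |

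The intervals are wide in any case: the upper limit is about 7.5 times the lower.

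**The case against.** The case on the other side has five parts.

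- **The Cox model already shows the harm.** The plan has "tolerability measured via retention time", so an excess of early exits on bupropion would be reported. A reader might infer that the AE analysis could conceal harm altogether; the documents do not support that. What remains is that the Cox result leaves the AE contrast and its interval as they were.
- **AEs have other routes into the data.** Participants keep a diary that covers side effects (Initial Treatment Visit), and diaries are collected at each visit (Medication Compliance Monitoring), so an isolated missed visit need not lose AEs. The one- and three-month contacts could recover AEs from leavers. This stands in part: they help only if leavers are reached and those AEs are counted, and neither is stated.
- **Tolerability is not a numbered aim.** A reader might take it for one of the trial's two aims, because the title pairs efficacy with safety and Research Approach pairs efficacy with tolerability. Overall Concept, however, numbers the aims as an efficacy signal and modulation by nicotine dependence, and Outcome Variables does not list AEs among the key outcomes. This limits the weight of the point.
- **The trial is exploratory and not powered.** That excuses wide intervals but not mis-centred ones. It does make lost power a poor yardstick, and a power comparison would also mix two changes. Take 2 AEs per 12 weeks on placebo, overdispersion 0.7, 30% v 10% leaving at week 4, and a true ratio of 2.0. An excess is then shown in 27% of trials by a Wilcoxon stand-in for the ordinal model, 43% by a negative binomial model without offset, and 66% with it. So (43 - 27)/(66 - 27), about two-fifths of the gap, comes from the model family and not from exposure.
- **An offset has its own bias.** With front-loaded AEs it over-corrects, as the last column of the first table shows. This stands, and it is the reason for reporting the offset model beside the ordinal model and not in its place.

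**Conclusion.** The point holds conditionally. As written, the AE analysis makes no allowance for time observed. If dropout differs between arms, the contrast favours the arm with more dropout.

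The tempting stronger reading is that bupropion will look safer than it is. The documents do not support it: they give no dropout figures, and the bias reverses if placebo loses more people (OR 1.31-1.42 at 30% v 10%). With equal dropout and equal rates there is none.

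The size rests on assumed dropout, AE rates and AE timing, and on counting AEs only up to exit. At equal true rates and 10% v 30% dropout it is an OR of roughly 0.70-0.77, or 0.82-0.84 with front-loaded AEs. At 10% v 50% under a constant rate it is 0.48-0.58, and a true 30% excess then appears as an OR of 0.89-0.90. The efficacy analyses are unaffected. This is a gap in a secondary safety analysis that is worth closing.

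**What to change.** 1. Define the AE counting window: the treatment period, and whether AEs reported at the one- and three-month contacts count, for early leavers as well as completers.
2. Add a negative binomial model (or Poisson with robust standard errors) of the AE count, with log(days observed in that window) as offset. Report the rate ratio and 95% confidence interval with the same treatment and nicotine-by-treatment terms. Because medication can be held or stopped without participation clearly ending, say that the denominator is days observed and not days on drug.
3. Report this beside the planned ordinal result.
4. Because the offset assumes a roughly constant AE rate, also report either the AE rate in a fixed early window or time to first AE.

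The change takes a few sentences in the analysis plan and a little more analysis work. The visit records and calendar-style diaries already planned should supply the dates. If dropout proves similar in the two arms, the added analysis will show that the ordinal result was not distorted by unequal follow-up.
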